5.2 Toxicities and Dosing Delays/Dose Modifications

Any patient who receives one dose of pembrolizumab will be evaluable for toxicity. Each patient will be assessed for the development of toxicity according to the Time and Events Table (Section 6.4). Toxicity will be assessed according to the NCI Common Terminology Criteria for Adverse Events (CTCAE), version 4.03. Dose adjustments should be made according to the system showing the greatest degree of toxicity.

Dose modifications in strength are not permitted for pembrolizumab

Dosing delays for Pembrolizumab:

- No dose delays for pembrolizumab are needed for hematologic changes.

- With any grade 2 or higher **non-hematologic toxicity deemed to be related to pembrolizumab**, hold pembrolizumab and refer to section 5.2.1. If adverse event is not an event of interest and improves to grade 1 or better, pembrolizumab may be resumed.
- If non-hematologic toxicity does not improve to grade 1 or better in 12 weeks from prior dose, discontinue pembrolizumab.

5.2.1 **Events of interest for Pembrolizumab:**

Certain adverse events that are possibly immune mediated warrant special monitoring and management, and are outline below to guide investigators.

5.2.1.1 **Pulmonary:**

Rule out non-inflammatory causes. If non-inflammatory cause, treat accordingly and continue protocol therapy. Evaluate with imaging and pulmonary consultation.

Grade of pneumonitis (NCI CTCAE v4.03)	Management	Follow-up
Grade 1 Radiographic Changes Only	
 • Consider delay of pembrolizumab • Monitor for symptoms every 2-3 days • Consider pulmonary and infectious disease consultations 	
 • Re-image at least every 3 weeks • If worsening, treat as grade 2, 3 or 4
Grade 2 Mild to moderate new symptoms	
 • Delay pembrolizumab • Consult pulmonary and infectious disease • Monitor symptoms daily, consider hospitalization • 1.0mg/kg/day methylprednisolone IV or oral equivalent • Consider bronchoscopy and/or lung biopsy 	
 • Re-image every 1-3 days • Consider prophylactic antibiotics while on steroids • If improves: 
 • When symptoms return to near baseline, taper steroids over at least one month • When steroids are at 10mg oral prednisone (or equivalent) or below, resume pembrolizumab • If not improving after 2 weeks or worsening, treat as grade 3 or 4

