Grade 3 
 Diarrhea ≥ 7 stools per day over baseline OR IV fluids needed for ≥ 24 hours due to diarrhea OR Colitis with severe abdominal pain or medical intervention indicated 	
 Delay pembrolizumab 1-2mg/kg/day methylprednisolone IV or IV equivalent Start prophylactic antibiotics for opportunistic infections such as PCP Consider lower endoscopy 	
 If improves 
 Continue steroids until symptoms are grade 1, then taper over at least one month Resume pembrolizumab if the event improves to grade 0 or 1 within 12 weeks and corticosteroids have been reduced to the equivalent of ≤ 10mg oral prednisone per day If persists for >3-5 days or recurs after improvement, add infliximab 5mg/kg if no contraindication (Note: infliximab should not be used in cases of perforation or sepsis)
Grade 4 Life threatening or perforation	
 Discontinue pembrolizumab 1-2mg/kg/day methylprednisolone IV or IV equivalent Start prophylactic antibiotics for opportunistic infections such as PCP Consider lower endoscopy 	
 If improves 
 Continue steroids until symptoms are grade 1, then taper over at least one month If persists for >3-5 days or recurs after improvement, add infliximab 5mg/kg if no contraindication (Note: infliximab should not be used in cases of perforation or sepsis)

5.2.1.3 Endocrinopathy:

Rule out non-inflammatory causes. If non-inflammatory cause, treat accordingly and continue protocol therapy. Consider visual field testing, endocrinology consultation and imaging.

Endocrinopathy	Management	Follow-up
Asymptomatic thyroid-stimulating hormone (TSH) elevation	
 Continue pembrolizumab If TSH <0.5 x LLN or TSH >2x ULN, or consistently out of range in subsequent measurements, include free T4 in subsequent measurements as clinically indicated Consider endocrinology consult 	
Symptomatic Hypothyroidism	
 Initiate thyroid replacement 	
Symptomatic Hyperthyroidism	
 Delay pembrolizumab Consider endocrinology consult Initiate anti-thyroid drug 	
 Resume pembrolizumab when symptoms of hyperthyroidism are controlled and thyroid function is improving

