Hypophysitis	
 Administer corticosteroids and hormone replacement as clinically indicated Delay pembrolizumab for grade 2 or 3 hypophysitis Permanently discontinue pembrolizumab for grade 4 hypophysitis 	
Symptomatic Adrenal Insufficiency	
 Delay pembrolizumab Administer methylprednisolone 1-2 mg/kg/day IV followed by oral prednisone 1-2mg/kg per day or equivalent once symptoms improve Add prophylactic antibiotics for opportunistic infections 	
 If improves to \leq grade 1, taper steroids over at least one month Resume pembrolizumab if the event improves to grade 0 or 1 within 12 weeks and corticosteroids have been reduced to the equivalent of \leq10 mg oral prednisone per day and the patient is on stable replacement therapy if required

5.2.1.4 Hepatic:

Rule out non-inflammatory causes. If non-inflammatory cause, treat accordingly and continue protocol therapy. Consider imaging for obstruction.

Grade of Liver Test Elevation (NCI CTCAE v4.03)	Management	Follow-up
Grade 1 AST or ALT >ULN to 3x ULN and/or total bilirubin >ULN to 1.5x ULN	
 Continue pembrolizumab 	
 Continue liver function test monitoring per protocol If worsening, treat as grade 2,3, or 4
Grade 2 AST or ALT >ULN to 3-5x ULN and/or total bilirubin >ULN to 1.5-3x ULN	
 Delay pembrolizumab Administer corticosteroids at a dose of 1-2mg/kg/day oral prednisone 	
 Resume pembrolizumab if returns to baseline If persists >5-7 days or worsens, treat as grade 3 or 4

Grade 3 or 4 AST or ALT >5x ULN and/or total bilirubin >3x ULN	
 Discontinue pembrolizumab Increase frequency of monitoring to every 1-2 days 1-2mg/kg/day methylprednisolone IV or IV equivalent for grade 3 and 2 mg/kg/day methylprednisolone IV for grade 4 Add prophylactic antibiotics for opportunistic infections like PCP Consult gastroenterologist 	
 If improves to grade 2, taper steroids over at least one month If does not improve within 3-5 days or worsens after improvement: 
 Add mycophenolate mofetil 1g twice daily If no response within an additional 3-5 days, consider other immunosuppressive agents per local guidelines
---	--	---

5.2.1.5 Pancreatic:

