	
 • 1-2mg/kg/day methylprednisolone IV or IV equivalent • Add prophylactic antibiotics for opportunistic infections 	
--	--	--

5.2.1.7 Renal:

Rule out non-inflammatory causes. If non-inflammatory cause, treat accordingly and continue protocol therapy

Grade of elevation in serum creatinine (NCI CTCAE v4.03)	Management	Follow-up
Grade 1 Serum creatinine >ULN and >baseline but ≤1.5x baseline	
 • Continue pembrolizumab • Monitor serum creatinine weekly 	
 • If returns to baseline, resume creatinine monitoring per protocol • If worsens, treat as grade 2, 3, or 4
Grade 2 or 3 Serum creatinine 1.5x baseline to ≤ 6 x ULN	
 • Delay or discontinue pembrolizumab • Monitor serum creatinine every 2-3 days • 0.5-1 mg/kg/day methylprednisolone IV or oral equivalent • Add prophylactic antibiotics for opportunistic infections • Consider renal biopsy 	
 • If improves to grade 1 
 • Taper steroids over at least one month • Resume pembrolizumab if improves to ≤ grade 1 within 12 weeks and corticosteroids have been reduced to ≤ 10 mg oral prednisone or equivalent per day • If elevation persists >7 days or worsens, treat as grade 4
Grade 4 Serum creatinine <6x ULN	
 • Discontinue pembrolizumab • Monitor serum creatinine daily • 1-2mg/kg/day methylprednisolone IV or IV equivalent • Add prophylactic antibiotics for opportunistic infections • Consult nephrology • Consider renal biopsy 	
 • If improves to grade 1 
 • Taper steroids over at least one month • Resume pembrolizumab if improves to ≤ grade 1 within 12 weeks and corticosteroids have been reduced to ≤ 10 mg oral prednisone or equivalent per day

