5.2.1.8 Infusion Related Reactions

Pembrolizumab can cause severe or life-threatening infusion-related reactions, including hypersensitivity and anaphylaxis, which have been reported in 6 (0.2%) of 2799 patients receiving Pembrolizumab.

Monitor patients for signs and symptoms of infusion-related reactions including rigors, chills, wheezing, pruritus, flushing, rash, hypotension, hypoxemia, and fever.

For severe (Grade 3) or life-threatening (Grade 4) infusion-related reactions, stop infusion and permanently discontinue pembrolizumab

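### The renal grade 4 row tells the investigator to discontinue pembrolizumab and, in its follow-up cell, to resume it

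*Combined protocol and SAP*

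**What the plan says.** Section 5.2.1.7 (Renal) sets out management and follow-up by creatinine grade.

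- Grade 4, management: "Discontinue pembrolizumab • Monitor serum creatinine daily", with methylprednisolone, prophylactic antibiotics and a nephrology consult. No delay is offered.
- Grade 4, follow-up: on improvement to grade 1, taper steroids and "Resume pembrolizumab if improves to ≤ grade 1 within 12 weeks", once steroids are at or below 10 mg prednisone equivalent per day.
- Grade 2 or 3: management allows either delay or discontinuation, and follow-up carries the same resume sentence. It also routes some patients onward: "If elevation persists >7 days or worsens, treat as grade 4".

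The general rules in section 5.2 are "If adverse event is not an event of interest and improves to grade 1 or better, pembrolizumab may be resumed" and "If non-hematologic toxicity does not improve to grade 1 or better in 12 weeks from prior dose, discontinue pembrolizumab". Section 5.2.1 describes its tables as guidance for investigators.

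**The concern.** The two cells of the grade 4 row give opposite instructions on the decision that matters most after a grade 4 event: whether the patient may receive the drug again. An investigator who works from the management cell stops for good. One who works from the follow-up cell restarts when the two conditions are met. Both would be following the row. At stake are re-exposure after the highest renal grade in the table and consistent handling between patients.

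**Working it through.** No arithmetic from the plan is involved. The check is a reading of the renal row against the general rule and against every other row in section 5.2.1.

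**Step 1: does section 5.2 settle it?** No. Its permission to resume is limited to events that are not events of interest, and renal toxicity is listed among the events of interest. Its other rule makes discontinuation the outcome when a toxicity has not reached grade 1 within 12 weeks. There, discontinuing is what happens instead of resuming. Temporary stops are called holds or delays.

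**Step 2: the discontinue-only rows.** These are the rows whose management cell offers discontinuation and no delay.

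| Row | Resume clause in follow-up |
|---|---|
| Pneumonitis grade 3 or 4 | None in the visible part; cell cut off in the text available |
| Diarrhea/colitis grade 4 | None |
| Hepatic grade 3 or 4 | None |
| Pancreatic grade 4 or recurrent | None |
| Neurological grade 3 or 4 | None |
| Meningitis or encephalitis | None |
| Renal grade 4 | Present |

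Count: 5 with none + 1 not fully readable + 1 with a clause = 7.

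**Step 3: the rows with a 12-week resume clause.** These are colitis grade 2, colitis grade 3, adrenal insufficiency, pancreatic grade 2 or 3, skin grade 1-2, skin grade 3-4, renal grade 2 or 3, and renal grade 4, which makes 8. Seven of them offer a delay (for skin grade 1-2 the delay is in the follow-up cell). Renal grade 4 does not.

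**Step 4: the closest comparison.** In the colitis table, grades 3 and 4 share their steroid and infliximab text. Grade 3 is a delay and has a resume line. Grade 4 reads "Discontinue pembrolizumab 1-2mg/kg/day methylprednisolone IV or IV equivalent" and has none. The step from delay to discontinue removes the resume line there; in the renal table it does not.

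**Step 5: the grade limit.** The grade 2 or 3 row runs up to and including 6 x ULN. The grade 4 row is printed as below 6 x ULN, which overlaps it. If grade 4 is to follow on from grade 3, the limit has to be above 6 x ULN. This matters for the repair: a permanent stop tied to the limit as printed would also catch patients in the grade 2 or 3 range.

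**The case against.** **Discontinue may not mean permanently.** The protocol says "Permanently discontinue pembrolizumab for grade 4 hypophysitis" and, for severe infusion reactions, "stop infusion and permanently discontinue pembrolizumab", so plain discontinuation could be read as reversible. But none of the seven discontinue-only rows uses the word permanently, so its absence does not set renal grade 4 apart. If plain discontinuation is reversible, the five other rows that can be read in full lack a restart rule.

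**Follow-up should be read subject to management.** The skin grade 3-4 row requires discontinuation for Stevens-Johnson syndrome or toxic epidermal necrolysis, yet its resume line makes no exception for them. A sensible reader applies that line only to patients who were delayed. This stands in part: the tables do sometimes need that reading. But the skin row also offers a delay, so its resume line has patients to apply to. The renal grade 4 management cell offers none.

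**The clause may be meant for escalated grade 2 or 3 patients.** Elevations lasting more than 7 days are sent to this row, and those patients may only have been delayed. This is plausible and cannot be excluded, but the row does not say so and its heading is grade 4.

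**Other provisions protect the patient.** Section 5.6 ends treatment for unacceptable adverse events or on the investigator's judgment, section 5.7 then takes the patient off protocol therapy, and section 9.1 defers to the package insert for warnings. Resuming is conditional and the tables are guidance. All of this stands and limits the consequence. None of it says which renal cell governs.

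**Conclusion.** The point holds as a contradiction within one safety rule, to be corrected at the next opportunity. Its size is one row: the only one of seven discontinue-only rows with a visible resume clause. It rests on reading discontinue as section 5.2 uses it, and on both renal cells being complete, which they appear to be. The pneumonitis cell cannot be checked in full, so no claim is made about it.

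Three stronger readings are tempting and unsupported.

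- A reader might infer that re-exposure after grade 4 is forced. It is not, given the conditions, the guidance status of the tables and section 5.6.
- A reader might infer a copying error from the grade 2 or 3 row. The identical wording suggests it, but the documents do not show which cell was intended.
- A reader might infer a bias in the primary endpoint, since a restart could affect completion of four cycles within 15 weeks. The documents give no incidence for these events, so no effect on the 14 of 20 decision can be claimed.

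Nor do the documents settle whether a grade 2 or 3 elevation lasting more than 7 days should allow resumption. That is a clinical choice for the sponsor to state.

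**What to change.** In the renal grade 4 row, delete the resume bullet, write *Permanently discontinue pembrolizumab*, and give the limit as serum creatinine above 6 x ULN. The word permanently is already in the protocol for grade 4 hypophysitis and grade 3 or 4 infusion reactions.

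If the sponsor does intend re-exposure after a grade 4 renal event, change discontinue to delay in the management cell, keep the two resume conditions, and correct the limit in the same way.

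The sponsor should also say whether a grade 2 or 3 elevation treated as grade 4 because it lasted more than 7 days may resume.

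The cost is a wording change to one table row plus that clarifying statement, at the next amendment. It needs no extra patients, visits or analyses.

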5.2.1.8 Infusion Related Reactions

Pembrolizumab can cause severe or life-threatening infusion-related reactions, including hypersensitivity and anaphylaxis, which have been reported in 6 (0.2%) of 2799 patients receiving Pembrolizumab.

Monitor patients for signs and symptoms of infusion-related reactions including rigors, chills, wheezing, pruritus, flushing, rash, hypotension, hypoxemia, and fever.

For severe (Grade 3) or life-threatening (Grade 4) infusion-related reactions, stop infusion and permanently discontinue pembrolizumab

5.3 Stereotactic Body Radiotherapy

Stereotactic body radiotherapy (SBRT) involves advanced planning and delivery techniques to administer ablative doses of radiation to a target in a small number of fractions (treatment sessions). This has radiobiologic advantages and has been shown to be safe in numerous settings. A high priority is placed on minimizing exposure to surrounding normal tissues. Patients on this protocol will receive between three and five fractions of treatment. The dose per fraction will be determined per standard clinical practice and will be dependent on the location of the treated site and the adjacent organs at risk. SBRT will commence no later than initiation of the second cycle of pembrolizumab.

Both 3D-conformal radiotherapy and intensity-modulated radiotherapy (including volumetric arc radiotherapy [VMAT]) are acceptable planning techniques. Daily image guidance is required for this study.

5.3.1 Dose and Fractionation

The 3-fraction regimen will employ a minimum fraction size of 8 Gy and the 5-fraction regimen will employ a minimum fraction size of 6 Gy. Dose and fractionation will be determined per standard clinical practice and will be dependent on the location of the treatment site and adjacent organs at risk (i.e. to respect normal tissue tolerances).

Dose rate: For the purposes of this protocol, dose rate will be that which is commissioned by the manufacturer and the medical physics group for external beam radiotherapy delivery by the University of Michigan. There will be no special dose rate modifications required for this study.

5.3.2 Localization, Simulation, and Immobilization

Patients will be immobilized in an appropriate position to isolate the target lesion and will then undergo CT-based treatment planning. The CT scan must capture the region of interest as well as surrounding organs at risk (OAR) with adequate margin for treatment planning. The CT scan should be obtained with a uniform slice thickness of less than or equal to 3 mm. The use of IV contrast is at the discretion of the treating physician.

All lesions with the potential for respiratory motion should be evaluated by appropriate means, such as with a 4D-CT scan and/or implanted beacon(s)/marker(s). Respiratory motion management, including—but not limited to—methods such as breath hold, respiratory gating, and fiducial marker tracking, will be employed for applicable patients per standard clinical practice.

Daily image guidance will be employed for target localization. Typically this will include volumetric imaging (cone-beam CT) when possible, as well as any additional techniques deemed helpful.

5.3.3 Target Volumes

The gross tumor volume (GTV) is defined as all known gross disease corresponding to the selected lesion as visualized on the planning CT scan and aided by any additional relevant imaging studies (e.g. additional CT scans, PET/CT, MRI, etc.). The use of additional diagnostic imaging studies is dependent on the location of the lesion and is left to the discretion of the treating physician. An internal target volume (ITV) is defined for mobile lesions at the discretion of the treating physician. A 4D-CT scan will be acquired in order to account for the motion of the lesion if necessary. Breath hold techniques are also acceptable. For moving lesions, the ITV will be defined as the union of the visualized lesion on all gated CT datasets.

The clinical target volume (CTV) will equal the GTV/ITV with additional margin added to account for subclinical disease extension where appropriate as per standard practice. In the case of a lung metastasis, for example, the CTV would generally be equal to the GTV/ITV, whereas for a bone metastasis a margin may be added to account for disease that may extend further into the marrow than visible on imaging.

The planning target volume (PTV) will be defined as per the convention for photon beam radiotherapy. A 3-dimensional margin will be created on the CTV to allow for daily set-up variation.

5.3.4 Normal Structures

Organs at risk (OARs) in the vicinity of the target lesion will be delineated as visualized on the planning CT scan. When applicable, an expansion of 1-5 mm may be used to generate a planning organ-at-risk volume (PRV) to account for setup uncertainty and motion.

5.3.5 Treatment Planning

Acceptable planning techniques include 3D-conformal radiotherapy and intensity-modulated radiotherapy (including volumetric arc radiotherapy [VMAT]). For 3D-conformal radiotherapy, static 3D coplanar and/or non-coplanar beam arrangements as well as dynamic conformal arcs are permitted.

In the case of 3D coplanar or non-coplanar beam arrangements, these plans will be customized for each case to deliver highly conformal prescription dose distributions. Non-opposing, non-coplanar beams are frequently advantageous. Often, ≥ 7 -10 beams of radiation will be used with roughly equal weighting. More beams are typically used for larger lesion sizes. When static beams are used, a minimum of 7 non-opposing beams is encouraged. For arc rotation techniques, a minimum of 340 degrees (cumulative for all beams) is encouraged.

In order to obtain acceptable coverage for 3D conformal techniques, field aperture size and shape should generally correspond nearly identically to the projection of the PTV along a beam's eye view (i.e., no additional "margin" for dose buildup at the edges of the blocks or MLC jaws beyond the PTV). An exception should be when observing the minimum field dimension when treating small lesions. As such, prescription lines covering the PTV will typically be the 60-90% line for 3D conformal plans (where the maximum dose is 100%); however, higher isodoses (hotspots) must be manipulated to occur within the target and not in adjacent normal tissue. The treatment isocenter or setup point in stereotactic coordinates will be determined from system fiducials (and can be adjusted pre-treatment depending on the results from localization imaging studies) and translated to the treatment record.

All dose calculations will include corrections for tissue heterogeneities as specified by IROC Houston.

Maximum Dose:

The treatment plan should be created such that the maximum point dose (to a volume of at least 0.03cc) is $\leq 130\%$ of the prescription dose. This point must exist within the PTV.

Prescription Isodose:

This is variable, but for 3D conformal plans the prescription isodose surface will typically be 60-90% of the maximum dose.

Prescription Isodose Surface Coverage:

The prescription isodose surface will, ideally, be chosen such that $\geq 95\%$ of the target volume (PTV) is conformally covered by the prescription isodose surface (PTV V(Rx dose in Gy) $\geq 95\%$) and $\geq 99\%$ of the PTV receives a minimum of 90% of the prescription dose (PTV V(90%Rx dose in Gy) $\geq 99\%$). Additionally, every effort should be made to ensure that 100% of the GTV/ITV should receive $\geq 100\%$ of the Rx dose when possible. However, target coverage will be a priority 2 planning goal, and will therefore be secondary to priority 1 goals for critical organs at risk.

- (i) High dose spillage: The cumulative volume of all tissue outside the PTV receiving a dose $> 105\%$ of prescription dose should be no more than 15% of the PTV volume. Conformality of PTV coverage will be judged such that the ratio of the volume of the prescription isodose to the volume of the PTV is ideally < 1.2 . This may not be possible for very small tumors (< 2.5 cm axial CTV dimension or < 1.5 cm craniocaudal CTV dimension) due to the required minimum field size.
- (ii) Intermediate dose spillage: The falloff gradient beyond the PTV extending into normal tissue structures must be rapid in all directions and should ideally meet the following (suggested) criteria:

Location:

The maximum total dose over all fractions in Gray (Gy) to any point 2 cm or greater away from the PTV in any direction should be no greater than D_{2cm} where D_{2cm} is given by the table below.

Volume:

The ratio of the volume of the 50% isodose volume to the volume of the PTV ($R_{50\%}$) should meet the criteria in the table below if possible (adapted from RTOG 0915), although in some cases this may not be achievable. This table is used for all prescription requirements irrespective of calculation algorithm and total treatment dose.

Table 1: Conformality of Prescribed Dose for Calculations Based on Deposition of Photon Beam Energy in Heterogeneous Tissue

PTV Volume (cc)	Ratio of Prescription Isodose Volume to the PTV Volume		Ratio of 50% Prescription Isodose Volume to the PTV Volume, $R_{50\%}$		Maximum Dose (in % of dose prescribed) @ 2 cm from PTV in Any Direction, D_{2cm} (Gy)	
	Ideal	Good	Ideal	Good	Ideal	Good
	1.8	<1.2	<1.5	<5.9	<7.5	<50.0
3.8	<1.2	<1.5	<5.5	<6.5	<50.0	<57.0
7.4	<1.2	<1.5	<5.1	<6.0	<50.0	<58.0
13.2	<1.2	<1.5	<4.7	<5.8	<50.0	<58.0
22.0	<1.2	<1.5	<4.5	<5.5	<54.0	<63.0
34.0	<1.2	<1.5	<4.3	<5.3	<58.0	<68.0
50.0	<1.2	<1.5	<4.0	<5.0	<62.0	<77.0
70.0	<1.2	<1.5	<3.5	<4.8	<66.0	<86.0
95.0	<1.2	<1.5	<3.3	<4.4	<70.0	<89.0
126.0	<1.2	<1.5	<3.1	<4.0	<73.0	>91.0
163.0	<1.2	<1.5	<2.9	<3.7	<77.0	>94.0

Critical Organ Doses:

Critical organ dose-volume limits will be those used in standard practice at the University of Michigan.

Planning Priorities:

Every attempt will be made to successfully satisfy all of the planning goals and OAR criteria. In some circumstances, it may not be possible to meet all the ideal criteria. In these cases, spinal cord, cauda equina, sacral plexus (when applicable), and brachial plexus dose constraints must be respected over PTV coverage. In the case of other OAR constraints, which are not well validated, PTV coverage and OAR constraints must be balanced per clinical practice at the discretion of the treating physician.

